**The TackSHS survey:
a cross-sectional study on secondhand smoke in 12 European countries**

NCT number: NCT02928536

Date: 3 May 2016

BACKGROUND AND RATIONALE

Secondhand tobacco smoke (SHS) is a complex mixture of thousands of compounds, including particulate matter emitted by the combustion of tobacco products and from smoke exhaled by smokers [1]. It contains about 70 chemicals recognized as known or probable human carcinogens, other animal carcinogens, and many toxic and irritant agents [2]. Over the past two decades, SHS has been shown to cause adverse health effects on adults and children, including heart diseases, cardiovascular and respiratory disorders, lung cancer and other selected neoplasms [1, 2]. Of the 5.7 million deaths attributable each year to tobacco smoking, more than 600,000 (i.e., around 1% of all deaths worldwide) refer to subjects who never smoked and that prematurely die due to their lifetime exposure to SHS [3, 4]. Consequently, the World Health Organization (WHO) in its Framework Convention for Tobacco Control (FCTC) states the need to develop smoke-free policies to protect non-smokers from the consequences of SHS [5]. According to various population-based cross-sectional surveys, it has been estimated that between 20% and 60% of European non-smokers are exposed to SHS [6-11]. However, important reductions in SHS exposure have been found in selected indoor settings, including workplaces and hospitality venues such as bars and restaurants [12], after the implementation of smoke-free legislations.

Electronic cigarettes (e-cigarettes), the most common “electronic nicotine delivery systems”, have erupted in the market over the last 5 years, and their sales and popularity have rapidly and considerably grown worldwide and across the European Union (EU).

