This task is included in the WP3 of the TackSHS Project. Once the fieldwork is completed, DOXA will collect data from its European partners, and, after internal checks, will provide to “Mario Negri” Institute, the 12 anonymous data files in text format, with the corresponding codebook in English language. The 12 data files will be managed by the expert biostatisticians at the Department of Epidemiology of “Mario Negri” Institute. Through the use of the statistical package SAS, version 9.4 (SAS Institute, Cary, NC, USA), they will perform the input of the 12 textual data file into 12 corresponding SAS datasets, and then create a unique final dataset SAS. This dataset will be checked for coherence and for the presence of possible errors, cleaned, and finalized through the generation of queries which will be addressed by DOXA and its European partners.

Statistical analyses for WP3

Statistical analyses required to achieve objectives related to WP3 will be conducted by expert biostatisticians at the Department of Epidemiology of “Mario Negri” Institute, using SAS statistical package.

Prevalence of current smokers and e-cigarette users, and prevalence of exposure to SHS and e-cigarette aerosol, will be estimated through univariate statistical analyses (i.e., descriptive statistics for categorical data, including absolute or relative frequencies), overall, by country, and in strata of selected demographic and socio-economic (individual and country-specific) characteristics.

Continuous variables (e.g., age at starting or quitting smoking, number of cigarettes smoked per day, number of e-cigarette puffs per day) will be summarized through the use of means and standard deviations. Alternatively, they will be categorized, and thus described through absolute or relative frequencies.

Multivariate analyses will also be considered to identify sub-groups of the population (e.g., young vs. other age groups, unemployed vs. other working status, low vs. high educated subjects) or clusters of countries (e.g., middle vs. high income countries, low vs. high TCS, low vs. high smoking prevalence) more frequently adopting selected tobacco-related behaviours or more frequently exposed to SHS. Thus, odds ratios (OR), and the corresponding 95% confidence intervals (CI), will be estimated through logistic regression models after adjustment for age, sex, socio-economic status, and other selected individual-level characteristics. Multi-level procedures will also be considered.

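### For SHS exposure, a common outcome, the odds ratio is the only adjusted measure WP3 names; it shows which groups are more exposed but not how much more often

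*Combined protocol and SAP*

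**What the plan says.** The section on statistical analyses for WP3 has two layers.

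- **Descriptive.** The plan says that "prevalence of exposure to SHS and e-cigarette aerosol, will be estimated through univariate statistical analyses". These are frequencies, to be given "overall, by country, and in strata of selected demographic and socio-economic (individual and country-specific) characteristics". No adjustment is mentioned.
- **Adjusted.** Multivariate analyses are to find population sub-groups, or "clusters of countries (e.g., middle vs. high income countries, low vs. high TCS, low vs. high smoking prevalence"), that are "more frequently exposed to SHS. Thus, odds ratios (OR), and the corresponding 95% confidence intervals (CI), will be estimated through logistic regression models". The models are fitted "after adjustment for age, sex, socio-economic status, and other selected individual-level characteristics". On clustering the text adds only: "Multi-level procedures will also be considered".

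No adjusted prevalence, prevalence difference or prevalence ratio is named. The same section applies these approaches to attitudes, perceptions and knowledge as well. The background section cites surveys in which "between 20% and 60% of European non-smokers are exposed to SHS".

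**The concern.** The question is put in terms of frequency: who is exposed more often. The adjusted answer will be on the odds scale. When an outcome is rare the two scales nearly agree, but on the plan's own background figure SHS exposure is not rare.

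The protocol wants the results to inform smoke-free legislation and to reach policy makers and other non-specialists. Such readers may well take an OR of 2 as twice as often exposed. The planned unadjusted prevalences do not remove the difficulty. They show the size of the crude contrast, while the OR is adjusted for age, sex, socio-economic status and more. An adjusted prevalence contrast cannot be recovered by setting one beside the other.

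**Working it through.** The plan gives no effect size for any determinant of exposure, so there is no planned figure to reproduce on this point. Its one design figure, a maximum standard error below 1.6% per country, does not enter.

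**Inputs**
- Reference prevalence p0: 20%, 40% and 60%. The two ends are those of the range in the background section.
- Comparisons of two prevalences, and an OR of 2: assumptions, for illustration only.
- Reference prevalences of 5% and 10%: assumptions, to show a rarer outcome.

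**Step 1. From prevalences to the OR.** OR = [p1/(1−p1)] / [p0/(1−p0)], with all values kept inside 20% to 60%:
- 20% against 30%: (0.30/0.70)/(0.20/0.80) = 1.71; prevalence ratio (PR) 1.5.
- 40% against 60%: (0.60/0.40)/(0.40/0.60) = 2.25; PR 1.5.
- 20% against 40%: (0.40/0.60)/(0.20/0.80) = 2.67; PR 2.0.
- 20% against 60%: (0.60/0.40)/(0.20/0.80) = 6.0; PR 3.0.

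**Step 2. From the OR back to prevalences.** p1 = OR·p0/(1−p0+OR·p0); PR = p1/p0; prevalence difference (PD) = p1−p0. For OR = 2:

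| p0 | p1 | PR | PD (points) | (OR−1)/(PR−1) |
|---|---|---|---|---|
| 5% (assumed) | 9.5% | 1.90 | 4.5 | 1.11 |
| 10% (assumed) | 18.2% | 1.82 | 8.2 | 1.22 |
| 20% | 33.3% | 1.67 | 13.3 | 1.50 |
| 40% | 57.1% | 1.43 | 17.1 | 2.33 |
| 60% | 75.0% | 1.25 | 15.0 | 4.00 |

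The last column shows by how much the relative excess is inflated if the OR is read as a PR. In the 60% row only the reference group lies inside the cited range; the comparison group is at 75%.

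**Step 3. Conditional and marginal ORs.** If the optional multi-level models are used, their ORs are conditional on the random effect. With an assumed random-intercept SD of 0.5 to 1.0 on the logit scale, a conditional OR of 2 becomes a marginal OR of about 1.93 down to 1.78. This effect is smaller than the one in Step 2, but it is a further reason not to convert an adjusted OR by hand using a crude prevalence.

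**The case against.** The case for leaving the plan as it is has real weight.

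- **Prevalences are planned.** A reader might infer that WP3 will report nothing but ORs. The same section rules that out: crude prevalences by country and stratum will be available, and crude ratios and differences follow from them. The gap is confined to adjusted contrasts.
- **The OR answers the stated question.** The models are meant to identify groups. For a given adjusted contrast in such a model, an OR above 1 means a higher adjusted prevalence. It misleads on size only if it is read as a ratio of prevalences, and the plan nowhere says it will be.
- **Comparability.** A reader might also infer that ORs from low- and high-exposure countries or settings cannot be compared and will show false heterogeneity. The documents do not support this. The country cluster is itself the contrast, and no comparison of ORs between clusters or settings is planned. ORs can be compared on the odds scale. If the OR were constant, the PR would be the measure that moved, as Step 2 shows.
- **The PR has limits of its own.** A PR of 1.5 is impossible above a reference prevalence of 1/1.5 = 66.7%, and it depends on coding. Exposure of 90% against 60% is a PR of 1.5, but non-exposure of 10% against 40% is a PR of 0.25. Making it the headline measure would be a debatable choice of scale.
- **The 20% to 60% range is borrowed.** It comes from earlier surveys of non-smokers. It is not a planning assumption for this general-population sample or for any one setting, and the background section notes falls in exposure in workplaces and hospitality venues.
- **Downstream work is untouched.** WP9 uses the prevalence of exposure, and WP10 takes evidence on exposure from the survey; neither is described as using these ORs.

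All of this stands and limits the point. None of it supplies an adjusted statement of how much more often a group is exposed.

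**Conclusion.** The point holds as a modest reporting improvement. WP3 names one adjusted measure, the OR, for an outcome that is common on the only prevalence range the protocol gives. The ORs are valid and show direction, but they do not convey the adjusted size of the contrast on the prevalence scale.

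With both groups inside 20% to 60%, a PR of 1.5 appears as an OR of 1.71 to 2.25. An OR of 2 read as a PR inflates the relative excess 1.5-fold at a 20% reference and 2.33-fold at 40%. The 4-fold figure at 60% requires exposure above the cited range.

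The size rests on two assumptions: that exposure in this survey resembles the cited range, and that readers take the OR as a multiple of prevalence. For settings where exposure is rare the gap is small, as the 5% row shows. It would go too far to call the planned ORs wrong.

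**What to change.** Keep the logistic models and the ORs. For outcomes with prevalence above about 10%, add to the WP3 section:

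- **Standardised prevalences.** For each level of the determinant, predict exposure for every respondent as if at that level, holding age, sex, socio-economic status and the other covariates as observed, and average the predictions. If a multi-level model is used, average over the random effect too.
- **Contrasts.** Give the prevalence difference and the prevalence ratio between levels, with 95% CIs, beside each OR. Showing both avoids resting the message on one scale.
- **Wording.** State that ORs are not to be read as prevalence ratios.

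The same reporting suits common responses in the attitude and knowledge analyses. No new data and no different model are needed. The cost is a little more analysis code and larger tables.

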The study methodology will be similar to a previous companion pan-European survey, conducted in 18 European countries in 2010 within an EU Seventh Framework Programme (FP7) Project, entitled “Pricing Policies And Control of Tobacco in Europe” (PPACTE; Grant Agreement HEALTH-F2-2009-223323) [21]. Briefly, in each country, the study sample will be representative of the general population aged 15 years and over in terms of age, sex, geographic area, and socio-economic characteristics. The multi-stage methodology will be used as the preferred sampling methodology. In the first stage, the primary unit of selection will be geographic area or voting centre. In the second stage, households or municipalities will be selected. In the last stage,

respondents will be chosen randomly, in order to be representative of the population. In those countries where adult respondents will be selected from electoral rolls, the quota method will be used to select minors (i.e., aged 15 to 17). Other methods, including stratified or simple sampling or quota methods, will also be accepted wherever it is not possible to conduct a multistage random sampling.

Selection of countries

For the present study, an appropriate sample of 12 European countries – all EU Member States (MS) – representing geographical, legislative and cultural variations across the EU, has been selected.

The selected European countries are the following: Bulgaria (BG), England (UK), France (FR), Germany (DE), Greece (GR), Ireland (IE), Italy (IT), Latvia (LV), Poland (PL), Portugal (PT), Romania (RO), and Spain (ES).

These countries were selected after taking into account several aspects, including: i) different geographical distribution; ii) different level of per capita income; iii) different national smoking prevalence [21]; iv) different adoption of tobacco control strategies at a national level (i.e., Tobacco Control Scale, TCS) [22]; v) different tobacco ban legislations [22]; vi) high population size; vii) inclusion in a previous PPACTE survey [21].

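### The only committed odds-ratio model names no country term, so pooled odds ratios for education or employment may be confounded by country

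*Combined protocol and SAP*

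**What the plan says.** The section on creation of the survey dataset has the coordinating centre read in the 12 country files "and then create a unique final dataset SAS".

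Statistical analyses for WP3 then describes two kinds of contrast together. One is between individuals: "young vs. other age groups, unemployed vs. other working status, low vs. high educated subjects". The other is between "clusters of countries (e.g., middle vs. high income countries, low vs. high TCS, low vs. high smoking prevalence"). For both, odds ratios with 95% confidence intervals "will be estimated through logistic regression models after adjustment for age, sex, socio-economic status, and other selected individual-level characteristics". The paragraph ends: "Multi-level procedures will also be considered". It does not say at which level, for which analyses, under what condition, or which result would lead.

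Prevalence, by contrast, is planned overall, by country and in strata, including strata of country-specific characteristics.

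Under Selection of countries, the 12 were chosen as "representing geographical, legislative and cultural variations across the EU". The criteria include "different level of per capita income; iii) different national smoking prevalence", together with tobacco control strategy and ban legislation.

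**The concern.** In a pooled logistic model without a country term, the odds ratio for a personal characteristic combines two things: the association among people in the same country, and the association across countries between how common the characteristic is and how common exposure is. Only the first answers whether, say, less educated people are more exposed. The second can raise, lower or reverse it.

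The selection criteria make large differences between countries in secondhand smoke exposure likely. The questionnaire also records each country's school-system structure, so education may differ between countries too.

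Investigating the determinants of exposure is a named WP3 objective, and this is the only odds-ratio model given for it. The same methods are to be used for attitudes and knowledge, and the Relevance section wants the results to guide smoke-free laws. With about 12,000 respondents, a confounded odds ratio would also look precise. An analyst could leave country out and still comply with the plan.

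**Working it through.** **The plan's own figure.** The only design figure is a maximum standard error below 1.6% for a country prevalence. Under simple random sampling with n = 1000, √(0.5 × 0.5 / 1000) = 1.58%, so it reproduces. No figure is given for the odds ratios.

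**Inputs.** From the documents: 12 countries, about 1000 respondents each, and exposure of 20% to 60% among European non-smokers across surveys (Background). Assumed, because the documents do not give them: each country's share with the characteristic, the spread of exposure between countries, and the correlation of the two across countries.

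**Step 1: the mechanism, in a deliberately extreme case.** Let half the countries have 25% low education and 20% exposure, and half 55% and 45%. Within each country education has no effect (true OR = 1).

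- Exposure, low education: (0.25 × 0.20 + 0.55 × 0.45) / 0.80 = 0.372
- Exposure, higher education: (0.75 × 0.20 + 0.45 × 0.45) / 1.20 = 0.294
- Pooled OR: (0.372 / 0.628) / (0.294 / 0.706) = 1.42
- Cells at n = 12,000: 1785, 3015, 2115 and 5085. SE of log OR = √(1/1785 + 1/3015 + 1/2115 + 1/5085) = 0.0395, so the 95% CI is 1.32 to 1.54
- With the education shares swapped between the two blocks, the pooled OR is 0.70

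**Step 2: a less extreme simulation.** Twelve countries of 1000; low-education share with mean 40% and SD 12 points; exposure with mean 32.5% and SD 10 points; no within-country effect; respondents sampled at random.

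| Correlation across countries | Median pooled OR | False positives at 5%, no country term | Stratified by country |
|---|---|---|---|
| 0 | about 1.00 | about 31% | about 5% |
| 0.5 | about 1.10 (5th to 95th percentile 0.98 to 1.28) | about 61% | about 5% |

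At zero correlation the pooled OR is centred on 1, but chance correlation among only 12 countries still inflates the error rate. If the SD of the education share is 6 points instead of 12, the median OR at correlation 0.5 falls to about 1.05.

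**Step 3: exposure spread evenly over 20% to 60%.** This treats the Background range as a between-country range. True OR = 1, no country term, pooled OR with 95% CI:

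| Characteristic (assumed range of share) | Correlation +1 | +0.5 | −1 |
|---|---|---|---|
| Low education, 20–60% | 1.31 (1.22–1.41) | 1.15 (1.06–1.23) | 0.76 (0.70–0.82) |
| Low education, 30–50% | 1.15 (1.06–1.23) | 1.07 (0.99–1.15) | 0.87 (0.81–0.94) |
| Unemployed, 5–20% | 1.25 (1.12–1.39) | 1.12 (1.00–1.25) | 0.79 (0.71–0.89) |

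For a young age group with a share of 13–17%, the OR stays between 0.95 and 1.05 and every interval covers 1. With a true OR of 1.5 and an education share of 20–60%, the pooled OR runs from 1.08 (correlation −1) to 1.89 (correlation +1).

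**Step 4: with country in the model.** Country indicators return 1.00 (about 0.92 to 1.08) when the truth is 1.0, and 1.50 (about 1.39 to 1.62) when it is 1.5, in every scenario. A country random intercept gives mean ORs of 1.00 at correlation 0.5 and 0.99 at correlation 1 when the truth is 1.0.

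**The case against.** The plan can be defended on four grounds.

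- **A suitable tool is named.** A multi-level model with a country intercept recovers the within-country odds ratio. This stands as far as it goes: country adjustment is optional and unspecified, not ruled out. But an option without a level, trigger or priority does not bind the analysis.
- **The covariate list is open, and multivariate work is itself only to be considered.** Not naming country differs from deciding to omit it. That is fair, although the open end of the list is expressly for individual-level characteristics.
- **Pooling is not stated in so many words.** The merged file would allow models by country. Pooling is still the natural reading, because the country-cluster contrasts in the same paragraph need several countries in one model. If those cluster terms sat beside the individual-level ones, they would absorb part of the difference between countries; the plan does not say whether they would.
- **The bias is conditional.** It needs national shares of the characteristic to be associated with national exposure among these 12 countries. The selection criteria concern geography, population size, income, smoking and policy, not education, employment or age structure.

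A reader might infer something stronger: that the plan excludes country, so that differences between countries will be read as effects of education, employment or age. The documents do not support that. They leave a multi-level route open and give no country-level shares from which to establish a bias, and in the calculation above age was barely affected. The 1.42 in Step 1 shows the mechanism in an extreme case and is not an estimate for this survey.

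**Conclusion.** The point holds in a limited form. The only committed odds-ratio model names individual-level covariates and no country term, and the remedy is left optional. Odds ratios for determinants such as education and employment may therefore be confounded by country, if they come from the merged dataset. Whether they would be, in which direction and by how much cannot be determined from the documents. Under the assumptions in Step 2, the typical distortion is modest (median OR 1.00 to 1.10), but the false-positive rate is well above 5%.

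Prevalence estimates and data collection are not affected. The change is a cheap improvement to the analysis plan and need not hold up the study.

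**What to change.** In Statistical analyses for WP3, state that every pooled odds ratio for an individual-level determinant includes country, either as fixed effects (11 indicators) or as a committed country random intercept, and is read as a within-country association. Either choice is acceptable; it should be made in advance.

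Estimate the contrasts by country income, TCS and smoking prevalence in a separate multi-level model with country-level covariates, with inference that reflects 12 countries. They are collinear with country fixed effects and cannot be estimated beside them.

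The cost is a sentence or two in the plan, a small loss of precision at about 1000 respondents per country, and slightly more analysis work. No new data are needed.

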The English version of the questionnaire (Annex 4) has been developed through the collaboration with the partners of the TackSHS consortium. Before fieldwork, DOXA and its European partners will translate the questionnaire, under the supervision of the TackSHS consortium, in various country-specific languages. Some questions are identical to those formulated in a previously conducted pan-European survey (the PPACTE survey), in order to allow comparisons in time.

The first part of the questionnaire includes country-specific data to be provided by DOXA and its European partners for each European country. These data include i) information on sampling methodology (e.g., sampling method used, response rate, fieldwork dates, age range), and ii) country-specific information (e.g., country population size, price of cigarette packs, gross domestic product, structure of the school system, and current policies regulating tobacco smoking and electronic cigarette use implemented at a national level, with a focus on indoor public/private places and transports, and outdoor public places).

The second part of the questionnaire is designed to collect individual-level information for each survey participant, and is divided in four sections:

- A. socio-economic and demographic characteristics (e.g., sex, age, level of education, and profession);
- B. cigarette smoking habit and e-cigarette use (e.g., smoking status, use of e-cigarette –and, in Italy, use of heat-not-burn tobacco cigarette-, smoking/vaping intensity and duration, and consequences of e-cigarette use on smoking behaviour);
- C. cigarette smoking, e-cigarette consumption, and SHS and e-cigarette aerosol exposures in different sites (e.g., exposure to SHS in indoor public places, workplaces, private venues, also in presence of minors, homes, transports, and selected outdoor places);
- D. attitudes and perceptions on smoke-free regulations and awareness of SHS harmful effects.

Statistical analysis plan

Creation of the survey dataset

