The aforementioned statistical approaches will be used also to describe: i) the attitudes and perceptions of the adult European population towards policies to control tobacco and to limit SHS exposure; and ii) the knowledge and beliefs of current smokers and the general adult population on the harmful effects of SHS.

To evaluate the changes in time of selected smoking-related aspects, including smoking prevalence and patterns, voluntary home smoking ban, and perceptions on the efficacy of smoking bans as tobacco control policies, TackSHS data will be compared with data from a previous companion European survey (the PPACTE survey). A unique SAS dataset including common variables will be created for the 11 European countries considered in both surveys (i.e., BG, UK, FR, GR, IE, IT, LV, PL, PT, RO, and ES). Significance of differences between the two survey periods will be performed both through univariate (χ^2 test for categorical variables and t-test for continuous ones) and multivariate analysis (regression models).

Statistical analyses for WP9

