“Mario Negri” Institute, a non-for-profit private institute, had no obligation at a national or EU level, to launch a call for tender to select the most suitable market research organization, since “Mario Negri” Institute is not a contracting authority/contracting entity. However, in respect of the current practice at EU level, “Mario Negri” Institute requested a series of quotations from selected research market institute before the project submission. The 6th of February 2015, formal quotes have been required by e-mail four leading research market institutes offering a network of representatives throughout Europe with trained surveyors (i.e., DOXA, GfK-Eurisko, IPSOS and TNS). For a scenario of a face-to-face survey with 1000 participants in each of 12 countries, 12-14 minutes of interview, DOXA quoted € 225,000 + VAT for completion of this work, GfK-Eurisko requested € 315,000 + VAT, IPSOS requested € 325,680 + VAT and TNS requested € 421,000 + VAT. Therefore, DOXA provided by far the lowest quotation. Moreover, “Mario Negri” Institute has been collaborating with DOXA for several years to carry out annual national surveys on smoking since 2001. Therefore, the collaboration has been established before the beginning of the project. More importantly, in 2010, within the PPACTE project, “Mario Negri” Institute, in collaboration with DOXA and its European partners, already conducted a face-to-face representative survey on economic aspects of smoking in 18 European countries, using the same sample size, sampling methodology, and population proposed for the present investigation. A specific objective of the TackSHS survey refers to the comparison between data provided by the new survey and PPACTE data. Having DOXA as a subcontractor assures the identical country-specific sampling methodology. This allows us to obtain a more accurate comparison of selected smoking characteristics.

On the basis of the quotes received, the “best value for money” principle, and the long lasting collaboration with the Department of Epidemiology of “Mario Negri” Institute, DOXA has been identified as the best provider for the service.

Secondary used database

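### The comparison with 2010 names standard tests and makes no provision for area-based multistage sampling; run in standard form, they understate the variance of a change wherever its design effect exceeds 1

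*Combined protocol and SAP*

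**What the plan says.** **The tests.** The last paragraph of Statistical analyses for WP3 sets out the comparison with 2010. On data, it says "A unique SAS dataset including common variables will be created for the 11 European countries considered in both surveys". For significance between the two periods it names a chi-square "test for categorical variables and t-test for continuous ones) and multivariate analysis (regression models").

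**The design of the new survey.** Study design says "The multi-stage methodology will be used as the preferred sampling methodology", and "In the first stage, the primary unit of selection will be geographic area or voting centre". Two exceptions follow. Where adults are drawn from electoral rolls, "the quota method will be used to select minors (i.e., aged 15 to 17"). More generally, "Other methods, including stratified or simple sampling or quota methods, will also be accepted wherever it is not possible to conduct a multistage random sampling".

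**The design of the 2010 survey.** The section on selecting the subcontractor says that it was run "using the same sample size, sampling methodology, and population proposed for the present investigation".

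**What comes nearest to a provision for clustering.** Earlier in the WP3 section, the paragraph on sub-groups and clusters of countries ends by leaving multi-level methods open as an option. The next paragraph carries those approaches over to attitudes and knowledge. The comparison with 2010 stands apart, with its own tests.

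**The concern.** A chi-square test, a t-test and an ordinary regression model treat respondents as independent. Respondents from the same area or voting centre tend to resemble each other, so an area sample of 1000 usually carries less information than 1000 independent draws. Where a country was sampled by area in both surveys, both sides of the comparison are clustered.

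If the variance of the change is understated, p-values for change in smoking prevalence, home smoking bans and perceived ban efficacy are too small. Chance differences would then be reported as changes more often than intended. The comparison is a listed WP3 objective and part of the reason given for choosing the subcontractor.

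**Working it through.** Below, D is the variance relative to simple random sampling.

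**1. The plan's own precision figure.** Sample size computation states a maximum standard error below 1.6 points per country, with about 1000 respondents.
- √(0.25/1000) = 1.58 points, so the figure reproduces under simple random sampling.
- It leaves room only for D up to (1.6/1.581)² = 1.024. No design effect was built in.

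**2. Inputs.**
- From the documents: about 1000 per country now; 18,056/18 = 1003 per country in 2010; 11 countries compared.
- Assumed, because the documents give none: a two-sided 5% level for this comparison; D of 1.2, 1.5 or 2.0 in each survey; m = 10 interviews per area; the share r of areas re-used with stable effects.

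**3. Within one country, independent areas.** True error = 2 × [1 − Φ(1.96/√D)]. SE of the change = √(2p(1−p)D/1000).

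| D | True error | SE, p = 50% | SE, p = 25% |
|---|---|---|---|
| 1.0 | 5.0% | 2.24 points | 1.94 points |
| 1.2 | 7.4% | 2.45 | 2.12 |
| 1.5 | 11.0% | 2.74 | 2.37 |
| 2.0 | 16.6% | 3.16 | 2.74 |

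Below 1 the tests are conservative: 2.8% at D = 0.8.

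**4. Areas re-used in both surveys.** D = 1 + (m − 1) × ICC, and D for the change = D − r × m × ICC. With m = 10, an ICC of 0.022, 0.056 or 0.111 gives D = 1.2, 1.5 or 2.0.

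| D in each survey | r = 0.5: D for change, error | r = 1: D for change, error |
|---|---|---|
| 1.2 | 1.09, 6.0% | 0.98, 4.7% |
| 1.5 | 1.22, 7.6% | 0.94, 4.4% |
| 2.0 | 1.44, 10.3% | 0.89, 3.8% |

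The break-even is r = (m − 1)/m, which is 0.90 here. A simulation (20,000 runs, 100 areas of 10, p = 50%) gave errors of 7.4%, 11.4% and 16.7% at r = 0; 6.3%, 7.7% and 10.9% at r = 0.5; and 5.0%, 4.7% and 3.8% at r = 1.

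**5. Pooled over 11 countries, independent areas.** The unadjusted test uses the overall p(1−p), which includes between-country spread that does not affect the change, because country sample sizes are fixed. Take an assumed mean of 40% and D = 1.5.
- Country SD of 10 points: within-country variance 0.24 − 0.01 = 0.23; effective D = 1.5 × 0.23/0.24 = 1.44; error 10.2%.
- Country SD of 15 points: 0.24 − 0.0225 = 0.2175; effective D = 1.36; error 9.3%.

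Simulation agrees, at about 9–10% against 11% within a country.

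**6. Which strata a corrected pooled test needs.** If areas differ between surveys and strata are countries alone, between-country differences enter the variance. The estimated variance is then too large by a factor of about 1 + m × SD²/(D × within-country variance).
- SD 10 points: 1 + 10 × 0.01/(1.5 × 0.23) = 1.29.
- SD 15 points: 1 + 10 × 0.0225/(1.5 × 0.2175) = 1.69.

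Simulations gave 1.25 to 1.34 and 1.6 to 1.69, with true error of 2.3–3.3% and 0.9–1.4%. Strata defined by country and survey period gave ratios of 0.98 to 1.04.

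**The case against.** **The plan is silent rather than wrong.** It names families of tests and does not rule out survey-adjusted versions. That is true. But an adjusted version needs area and stratum codes, and the documents do not say that the 12 data files or the merged dataset will hold them. Under the privacy procedures, addresses and other identifiers are deleted within four months of the end of data collection, so codes not written to the files by then may not be recoverable.

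**Multi-level methods are mentioned.** They are optional, name no level, are not attached to this comparison, and would not alter a chi-square test or t-test.

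**Neither size nor direction is known.** This stands. A reader might infer that the trend p-values will be too small, or that a design effect above 1 in each survey settles the matter. The documents support neither inference. They give no design effect, ICC or cluster size. The promise of the same country-specific methodology fits fresh areas or re-used ones, and re-use can offset nearly all of the inflation or more.

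**Not every country need be clustered.** This also stands. Simple, stratified and quota samples are allowed, and the formulas above do not describe quota samples, which have no design-based variance.

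**The same gap affects other results.** It does: the odds-ratio intervals and the stated standard error share it. That is a reason to widen the fix, not to drop the point.

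**Conclusion.** The point holds in conditional form. The plan makes area-based multistage sampling the preferred method in both surveys and names, for the comparison between them, tests with no provision for it. In area-sampled countries those tests in standard form understate the variance of the change wherever its design effect exceeds 1.

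The omission is certain; its effect is an assumed range. Within a country, with independent areas and D from 1.2 to 2.0, a nominal 5% test has a true error of 7.4% to 16.6%. With half the areas re-used the range is 6.0% to 10.3%, and with all re-used and stable there is no inflation. In a pooled test the inflation is somewhat smaller when country prevalences differ. The documents do not say whether change is tested by country, pooled or both. The change should be made, with medium confidence in how much it will matter.

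**What to change.** In the paragraph on the comparison with 2010, name design-based versions in the SAS package already planned: the Rao-Scott chi-square (SURVEYFREQ), SURVEYREG and SURVEYLOGISTIC. Use the primary unit as cluster, and weights where they exist. Set the strata by what happened to the areas:

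- **Areas differ between surveys:** strata by country and survey period, within any sampling strata.
- **Same areas re-used:** one cluster code across both surveys, within country strata, with country in the model. This keeps the covariance and keeps between-country differences out of the variance.

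Ask the subcontractor for non-identifying primary-unit and stratum codes in the 12 data files, and whether 2010 areas are re-used. The country-level part of the questionnaire already collects "information on sampling methodology (e.g., sampling method used, response rate, fieldwork dates, age range"), so the method can be tabulated by country beside the trend results.

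Where 2010 codes are not held, show results over a labelled range of assumed design effects, such as 1.0 to 2.0. For quota samples, including minors selected by quota, state that the variance is approximate. Apply the same variance method to the odds-ratio intervals in the WP3 section, and state under Sample size computation that the standard error (1.58 points) assumes simple random sampling.

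**Cost.** SAP wording and a few extra variables in the data files and codebook. Expect wider intervals and fewer significant changes. The documents do not say whether the 2010 file holds area codes or weights, so that side may rest on the labelled range.
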